9.7.3.3.2 Duration of Concomitant Medications

The duration of use of a CMI will be expressed in days.

The duration of concomitant medication use will be computed considering all CMI, by therapeutic class of CMI (CMI1 to CMI7), and for the group of CYP inhibitors (CMI1 to CMI4). Also, for patients that have taken a strong or moderate CYP2D6 inhibitor simultaneously with a strong or moderate CYP3A inhibitor, the duration of CMI overlap will be explored, if feasible.

For each CMI, the duration of CMI use will be computed in two steps. First, a total duration will be computed for each patient taking into account all deliveries belonging to the CMI category. Second, the average of the total duration for all patients will be computed together with its dispersion.

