9.2 Setting

9.2.1 Study Period

The study period will begin from one year before the first prescription of eliglustat in each data source to the end of the study.

The date of the first prescription of eliglustat will vary between data sources since the launching/reimbursement of eliglustat is different in each country (see Section 9.4). In any case, the first prescription will be after the date of approval of eliglustat by the EMA that is 19 January 2015.

The exposure period for one patient will be defined as the period between the exposure start date (date of the first record of eliglustat prescription) and the exposure end date, i.e., the date of the last eliglustat prescription plus the duration of eliglustat use according to the last prescription or the end of the study or the death of the patient if it occurs before the end of the study.

The end date of the study period will also vary between data sources since different time-lag exist between the time of prescription/delivery of drugs and availability of these data in databases. Consequently, in case of a two-year time-lag, data extracted in 2022 will have been collected until 2020 thus, the study period will end in 2020.

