9.7.1 General Considerations

The exposure period for one patient corresponds to the period of eliglustat use. This period will be defined as the period between the exposure start date (the first record of eliglustat prescription) and the exposure end date (end of study or date of the last eliglustat prescription plus the duration of eliglustat use according to the last prescription or death date).

The statistical analyses will be only descriptive and will include the following:

• Descriptive analysis of eliglustat therapy in terms of duration and dose.

- Descriptive analysis of the past medication use (one year prior to the exposure period) in terms of proportion, therapeutic class and duration. The treatments of interest will be (details in Appendix 1 in Section 14.1):
 - Strong and moderate CYP2D6 inhibitors (CMI1 and CMI2)
 - Strong and moderate CYP3A inhibitors (CMI3 and CMI4)
 - Simultaneous use of strong or moderate CYP3A inhibitors with strong or moderate CYP2D6 inhibitors (CMI1 + CMI2 + CMI3 + CMI4)
 - Strong CYP3A inducers (CMI5)
 - P-gp substrates (CMI6)
 - CYP2D6 substrates (CMI7)

The proportions will be computed taking into account all treatments of interest and also by type of treatments and by duration. Proportions for the group CYP inhibitors will be also computed. The duration will be treated as a continuous variable and also as a categorical variable. The categorical variable will be defined as follow: 1. Total use will be defined as any prescription whatever the duration; 2. Chronic use will be defined as total duration of single or consecutive prescriptions of 15 days or over.

If the number of GD1 patients allows it, stratified analyses based on gender and age groups will be performed as well as analyses by year.

- Descriptive analysis of the concomitant medication use (i.e., during the exposure period) in terms of proportion, therapeutic class and duration. The treatments of interest will be the same as for the past medication use. The proportions will be computed as for the past medication use that is considering all treatments and also by therapeutic class and duration.
- Descriptive analysis of the health care service pattern (i.e., prescriber's specialty and types of patient visit) for the use of concomitant medications.

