9.7.3.3 Concomitant Medications

To analyse the use of concomitant medications, two study periods will be determined:

- 1. The one-year period before the first delivery of eliglustat.
- 2. The period during eliglustat use which will span from the first delivery of eliglustat to the last delivery of eliglustat plus the duration of supply.

The analyses described in the following sections will be conducted separately for each of the two periods.

9.7.3.3.1 **Proportion of Patients with CMI**

Proportion of patients with CMI will be computed considering all CMI, by therapeutic class of CMI (CMI1 to CMI7), and separately for the group of CYP inhibitors (CMI1 to CMI4). Also, proportion of patients that have taken a strong or moderate CYP2D6 inhibitor simultaneously with a strong or moderate CYP3A inhibitor will be explored, if feasible.

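### Duration of concomitant medication use, as defined, can count a calendar day more than once, averages users with non-users, and takes no account of unequal time on eliglustat

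*Protocol*

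**What the plan says.** Section 9.1.1 makes CMI use before and during eliglustat a primary outcome. Section 9.7.3.3.2 gives its duration in days, for all CMI together, for each class CMI1 to CMI7, and for the pooled CYP inhibitors CMI1 to CMI4. The algorithm has two steps. The per-patient step reads: "a total duration will be computed for each patient taking into account all deliveries belonging to the CMI category". These patient-level figures are then summarised over the cohort, where the plan says that "the average of the total duration for all patients will be computed together with its dispersion". Concurrent use is mentioned only for a CYP2D6 inhibitor taken with a CYP3A inhibitor, where "the duration of CMI overlap will be explored, if feasible".

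The time frame is set just above, in Section 9.7.3.3. One period is the year before the first eliglustat delivery. The other is described as: "The period during eliglustat use which will span from the first delivery of eliglustat to the last delivery of eliglustat plus the duration of supply". On how the two are used, the same section states: "The analyses described in the following sections will be conducted separately for each of the two periods". Section 9.2.1 closes the exposure period with further limits, "or the end of the study or the death of the patient if it occurs before the end of the study", and Section 9.7.1 also names end of study and death. Section 9.7.3.3 does not repeat them.

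Duration also has a categorical form, in Sections 9.3.2 and 9.7.1: "Chronic use will be defined as total duration of single or consecutive prescriptions of 15 days or over".

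**The concern.** The study is meant to show whether avoidance of interacting drugs is working. The useful quantity is therefore the number of days on which a patient on eliglustat was covered by an interacting drug. The two-step definition does not clearly give that quantity, for four reasons.

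- **Overlap.** A total over all deliveries has no rule for two drugs of the same category held on the same days. The pooled groups give the most room for this.
- **Denominator.** An average for all patients puts zeros in for patients who never received the drug. The proportion of users, already reported under Section 9.7.3.3.1, is then folded into the duration.
- **Time at risk.** An absolute number of days grows with time on eliglustat. It cannot be compared between patients or data sources with different follow-up, or between the fixed one-year period before eliglustat and the open-ended period during it.
- **Period limits.** Nothing says how much of a supply counts when it starts before a period limit and runs past it.

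Overlap pushes the reported figure up and zeros push it down, so a reader could not tell even the direction of the error.

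**Working it through.** The protocol states no figure for CMI duration, so there is none to reproduce. The only document figure used as a rate is the pilot's user share (Appendix 3): 10/48 = 20.8%, as printed there. All dispensing patterns below are assumptions chosen to show size.

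**1. Overlap.** Two drugs of one class are both held for D days.
- Sum of supplies = 2 × D; distinct calendar days = D.
- With D = 365: 730 against 365.
- For two drugs the ratio runs from 1 (no overlap) to 2 (full overlap).
- One such patient adds 730 − 365 = 365 surplus days. Spread over the expected numbers in Section 9.5, the mean for all patients moves by 365/87 = 4.2 days (France), 365/20 = 18.3 (Israel), 365/11 = 33.2 (Germany) and 365/10 = 36.5 (Denmark).

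**2. Denominator.** Mean over all patients = user share × mean among users. At 10/48:

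| Mean among users (assumed) | Reported over all patients |
|---|---|
| 14 days | 2.9 |
| 30 days | 6.3 |
| 90 days | 18.8 |
| 365 days | 76.0 |

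The pilot covered a limited list of CYP inhibitors in patients on other Gaucher treatments. For other categories the share, and so the dilution, may differ. Section 9.7.3.3.2 itself restricts explicitly to takers when it describes the overlap of CYP2D6 and CYP3A inhibitors. The unrestricted average is therefore most naturally read as including non-users.

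**3. Unequal periods.** A patient is covered on 10% of days throughout (assumed). Total = 0.10 × 365 × years:
- 1 year: 36.5 days
- 2 years: 73.0 days
- 3 years: 109.5 days
- 5 years: 182.5 days

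With unchanged behaviour, this patient shows 36.5 days in the year before eliglustat and 109.5 days during three years on it. The percentage is 10% in both periods.

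**4. Period limits.** A 30-day supply delivered 10 days before the eliglustat period ends counts 30 days uncut and 10 days cut. A 30-day supply delivered 10 days before the first eliglustat delivery has 30 − 10 = 20 days inside the period. Assigned by delivery date alone, it contributes none of them.

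**5. The 15-day rule set beside the total.** Three separate 7-day courses total 3 × 7 = 21 days under Section 9.7.3.3.2. The longest run is 7 days, so the patient is not chronic under Sections 9.3.2 and 9.7.1 if consecutive means adjoining. The protocol sets no gap rule, and does not say whether consecutive prescriptions must be of one drug or may run across a class.

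**The case against.** The strongest reply is that the protocol defers detail. Sections 9.3 and 9.7 point to a SAP and country-specific dataset specifications, and rules for merging and cutting supplies commonly live there. That carries weight for the supply-cutting rule. It carries less for the rest, because Section 9.7.3.3.2 already fixes the total, the population averaged over and the absolute scale. Section 9.6 has variables built by local procedures in separate databases, while Section 9.7.1 intends comparison between countries, so a common rule matters.

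Second, taking all deliveries into account does not require a plain sum, since a count of distinct covered days also uses every delivery. This is correct. Summation is the likely reading, not the only possible one.

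Third, a mean among users can be recovered by dividing by the proportion of users (18.75 ÷ 10/48 = 90). This works for a mean when the proportion is printed. It does not give a median or quartiles, and it fails where Section 10.4 masks a small count.

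Three stronger inferences are tempting, and the documents do not support them.

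- **That duration is not confined to eliglustat time.** Section 9.7.3.3 runs every analysis separately in each of the two periods. Only the treatment of a supply crossing a limit is open.
- **That the total inflates chronic use.** Chronic use has its own definition, resting on single or consecutive prescriptions. Two supplies held at the same time are not consecutive.
- **That drugs listed twice in Appendix 1 are counted twice.** Fifteen drugs do appear in two lists, but reporting a drug under both classes is correct. Its days double only if class totals are added, which the protocol does not say. Within CMI1 to CMI4 this could affect only berotralstat and dronedarone.

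**Conclusion.** The point holds. The definition of CMI duration in Section 9.7.3.3.2 is a poor measure of time exposed to an interaction and should be changed. If supplies are summed, two fully concurrent drugs of a category double a patient's figure (730 against 365 days). If non-users count as zeros, the reported mean falls to about 21% of the mean among users at the pilot's share. Both conditions follow the plain reading of the text, but neither is spelled out. Independently of both, an absolute total is not comparable across periods of different length.

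How often concurrent use will occur is unknown. In the pilot, one of 48 patients used more than one of the listed inhibitors, concurrency was not shown, and substrates were not studied. The weakness affects the interpretation of one primary descriptive measure. It does not affect the proportion of users or the eliglustat dose and duration results.

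**What to change.** Amend Section 9.7.3.3.2, and carry the wording into the SAP and dataset specifications:

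1. Define duration as the number of distinct calendar days on which at least one drug of the category is in supply. Count each day once within a class and once in the all-CMI and CMI1 to CMI4 groups.
2. Cut supplies at both limits of each period, and add the death and end-of-study limits of Sections 9.2.1 and 9.7.1 to the period in Section 9.7.3.3.
3. Report the number of users, the median and interquartile range among users (the mean may be kept, with its denominator stated), and covered days as a percentage of eliglustat days. For the period before eliglustat, use 365 as the denominator.
4. For the 15-day rule, state whether consecutive prescriptions run within one drug or across a class, and reconcile Sections 9.3.2 and 9.7.1 with Section 9.7.3.3.2.

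The cost is a wording change and a little extra programming, using the delivery dates and supplies that the present definition already needs. No further data are required.

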9.7.4 Analysis of Secondary Endpoints

The secondary endpoints will be assessed considering the two study periods separately, as in Section 9.7.3.3.

9.7.4.1 Type of Prescribers for Concomitant Medications

Prescribers of CMI will depend on the data source and could include general practitioner, haematologist, oncologist, ophthalmologist, rheumatologist, surgeon, etc. A list of prescriber specialties will be identified. For each prescriber, numbers and proportion of patients having had at least one CMI delivery realised by this prescriber will be computed considering all CMI, by therapeutic class of CMI (CMI1 to CMI7) and for the group of CYP inhibitors (CMI1 to CMI4).

9.7.4.2 Type of Visit for Concomitant Medications

The visit types will depend on the data source and could include in city, in hospital, in specialised care centres, etc. A list of visit types will be identified. For each type of visit, numbers and proportion of patients having had at least one CMI delivery realised during this type of visit will be computed considering all CMI deliveries, by therapeutic class of CMI and for the group of CYP inhibitors (CMI1, CMI2, CMI3 and CMI4).

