8.2 Secondary Objective

The secondary objective of the DUS is to describe the healthcare service pattern (i.e., prescriber's specialty and types of patient visit) for the prescriptions of concomitant medications in patients treated with eliglustat. The relevance of prescriber's specialty and types of patient visit is to inform whether prescriptions to GD1 patients are made in hospital or in outpatients services, and to inform on the number of health professionals taking care of these patients.

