9.1.2 Secondary Endpoints

The secondary endpoints include prescriber's specialty corresponding to the delivered drugs (general practitioner [GP], haematologist, oncologist, ophthalmologist, rheumatologist, surgeon, etc.) and visit type corresponding to the delivered drug (e.g., in city, in hospital, in specialised care centres, etc.).

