9.3.2 Outcomes of Interest

Outcomes of interest include concomitant medication use in terms of therapeutic class and duration. The CMI are strong and moderate CYP2D6 inhibitors, strong and moderate CYP3A inhibitors, strong CYP3A inducers, P-gp substrates and CYP2D6 substrates. Simultaneous use of strong or moderate CYP2D6 inhibitors with strong or moderate CYP3A inhibitors concomitantly with eliglustat will be explored, if feasible. Other outcomes will be the prescriber's specialty and the type of patient visit (e.g., hospital or in outpatient settings).

Concomitant medication use will be identified using ATC codes available in each database.

The duration of drug use will be defined with a continuous variable (number of days) and also with a categorical variable. The categorical variables will be defined as follows: 1. Total use of concomitant medication will be defined as any prescription whatever the duration; 2. Chronic use of concomitant medication will be defined as total duration of single or consecutive prescriptions of 15 days or over.

Where information is available, and subject to Ethics Committee approval, data on prescriber's specialty will be defined as the specialty of doctors prescribing concomitant medications to GD1 patients (e.g., GPs, haematologists, neurologists, etc.). These data will enable to define the number and profile of health professionals managing these patients. Data on the type of patient's visit is intended to capture whether prescriptions of concomitant drugs to GD1 patients are written in hospital or in outpatient settings.

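### The secondary-endpoint tables count patients ever seen per specialty or visit type, so they cannot show how prescriptions of concomitant medications are distributed across settings and prescribers

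*Protocol*

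**What the plan says.** Section 8.2 of the Protocol sets the secondary objective as the healthcare service pattern "for the prescriptions of concomitant medications in patients treated with eliglustat". It gives two reasons. The first is about settings: "to inform whether prescriptions to GD1 patients are made in hospital or in outpatients services". The second is about how many clinicians are involved in care: "to inform on the number of health professionals taking care of these patients".

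Section 9.1.2 defines the secondary endpoints at the level of the delivery; visit type, for example, is the "visit type corresponding to the delivered drug". Section 9.3.2 says that visit type is meant to show "whether prescriptions of concomitant drugs to GD1 patients are written in hospital or in outpatient settings".

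The analysis rules are in 9.7.4. For specialty, 9.7.4.1 plans the "numbers and proportion of patients having had at least one CMI delivery realised by this prescriber". For visit type, 9.7.4.2 plans the "numbers and proportion of patients having had at least one CMI delivery realised during this type of visit". Both are produced for all CMI, by CMI class and for the CYP-inhibitor group (CMI1 to CMI4). Under 9.7.4 they are run separately for the two periods of 9.7.3.3: the year before the first eliglustat delivery, and the whole period of eliglustat use. The protocol plans no count or percentage of deliveries by setting or specialty, and neither rule states the denominator of the patient proportion.

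**The concern.** The objective and the endpoint definition speak of prescriptions and delivered drugs. The analysis rule speaks of patients, through a yes/no flag per category. A patient with 19 outpatient deliveries and 1 hospital delivery is flagged in both categories, exactly like a patient with 1 and 19. How much prescribing takes place in each setting is lost at that step.

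Sections 7.3 and 8 say the study serves to assess the risk minimisation measures, and 7.3 adds improving them. Where interacting drugs are prescribed, and by whom, bears on that. Section 9.7.1 also expects the source-by-source results to allow prescribing patterns to be compared between countries. A flag that accumulates over time is a poor basis for that comparison when observation time differs between sources.

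**Working it through.** The protocol gives no deliveries per patient and no setting shares, so it has no figure of its own to reproduce here. All patient sets, shares and delivery counts below are assumptions chosen to show how the rule behaves.

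**1. Can the planned table recover the distribution of prescriptions?** Take two sets of 20 CMI users with 20 deliveries each (400 deliveries per set).

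| | Set A | Set B |
|---|---|---|
| 10 users | 1 hospital + 19 outpatient | 19 hospital + 1 outpatient |
| other 10 users | 20 outpatient | 20 outpatient |
| Planned output, hospital | 10/20 = 50% | 10/20 = 50% |
| Planned output, outpatient | 20/20 = 100% | 20/20 = 100% |
| Hospital share of deliveries | 10/400 = 2.5% | 190/400 = 47.5% |

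The planned table is identical in both sets, and its categories add to 150%. This step needs no distributional assumption.

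**2. In which direction does the flag depart from the share?** Either.

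- *Deliveries spread over patients.* If a share s of deliveries is in hospital and a user has k independent deliveries, P(at least one in hospital) = 1 − (1 − s)^k. With s = 0.05: k = 1 gives 5%, k = 4 gives 1 − 0.95^4 = 18.5%, k = 10 gives 40.1%, k = 20 gives 64.2%. The flag lies above the 5% share once k exceeds 1.
- *Deliveries clustered in few patients.* Two users with 20 hospital deliveries each and 18 users with 5 outpatient deliveries each: the flag gives 2/20 = 10%, the delivery share is 40/(40 + 90) = 30.8%. One user with 10 hospital deliveries and 19 users with 5 outpatient deliveries each: 1/20 = 5.0% against 10/(10 + 95) = 9.5%. Here the flag lies below the share.
- *One delivery per user.* The two measures coincide.

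**3. Dependence on observation time.** For a given patient the flag can move from no to yes as time passes, never back. At an assumed 4 deliveries a year and a constant 5% hospital share, the scenario in step 2 gives 18.5% of users after one year (k = 4) and 64.2% after five (k = 20), with no change in prescribing. The first period of 9.7.3.3 is fixed at one year. The second is variable, and the duration categories in 9.7.3.2 run to two years and over. Between sources, 9.4 gives launch dates from April 2015 (Denmark, Germany) to 9 November 2016 (France) and 12 January 2017 (Israel), and data lags from none (Denmark, Israel) to up to two years (Germany). Available observation time therefore differs by source.

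The count of flagged patients can only rise with time. So can the proportion, if all eliglustat patients are the denominator. If the denominator is CMI users, newly entering users can dilute the rise. That is a further reason to state it.

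**The case against.** The strongest reply is that the objective nowhere asks for a percentage of prescriptions. Patient counts partly answer whether hospital or outpatient services prescribe, and the other stated purposes concern the number and profile of professionals managing these patients. One interacting prescription is enough to expose a patient, so knowing which specialties and settings ever prescribe is useful, notably for the patient alert card aimed at non-prescribers of eliglustat (7.3). This stands. A reader might infer that the patient is the wrong unit of analysis; the documents support only that it is incomplete.

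A reader might also infer that the rule generally overstates rare settings. It does not: step 2 shows the reverse under clustering, and repeat deliveries of a chronic drug may well come from one prescriber. The 18.5% and 64.2% are one scenario among CMI users. If the denominator were all eliglustat patients and inhibitor use matched the 20.8% of the pilot in Appendix 3 (patients on other Gaucher treatments), the CMI1 to CMI4 figures would be about 0.208 × 18.5% = 3.8% and 0.208 × 64.2% = 13.4%.

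Replacing the patient count by delivery shares would also be hard to defend. Section 9.5 expects 10 patients in Denmark, 11 in Germany and 20 in Israel, each source analysed separately. At 20.8% that is about 2, 2 and 4 inhibitor users, and one frequent refiller could set the percentage.

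Lastly, 9.7 defers detailed methods to the SAP and country-specific dataset specifications. The SAP was not available for this review and may add delivery-level tables. The protocol's own rule would still not match its objective.

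**Conclusion.** The point holds as a reporting gap in a descriptive secondary endpoint. The protocol frames the question around prescriptions and delivered drugs, but plans only overlapping patient-level flags. Those cannot recover the distribution of prescriptions: shares of 2.5% and 47.5% can give the same table. They can depart from a setting's share in either direction, and they accumulate with exposure time, so they are not comparable between the prior year and the eliglustat period, or between sources with different launch dates and lags.

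The non-identification rests on no assumption about the data. The size of the effect in this study is unknown: the 18.5% and 64.2% depend on an assumed 5% hospital share, assumed delivery counts and independence. No sample size or error rate is affected.

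**What to change.** In 9.7.4.1 and 9.7.4.2, keep the patient-level count and add beside it the number and percentage of CMI deliveries by specialty and by visit type. The denominator should be all CMI deliveries in the period concerned, with unknown as its own category. Do this for all CMI, by CMI1 to CMI7 and for CMI1 to CMI4. State the denominator of the patient-level proportion, and add a note that its categories overlap and need not sum to 100%.

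The cost is one extra column per table, from data already extracted. In the small sources a few heavy users can dominate the delivery percentages, so the two columns should be read together. A delivery share does not accumulate with time as the flag does, but patients followed longer carry more weight in it. Neither column removes the gap described in 9.4: drugs given during hospital stays are largely not captured in France and Germany, which contribute 87 + 11 = 98 of the 128 expected patients.
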